9.4. End Points

The following end points will be evaluated:

Primary outcome:

The primary outcome will be NHF use for 30 days following discharge after AECOPD. Use will be expressed as hours of myAIRVO 2 use per day over 30 days, as obtained by myAIRVO 2 electronic monitoring.

Secondary outcomes:

Other use variables:

- i. Number of days of use, adjusted for number of days with myAIRVO 2 at home
- ii. Average use per day of myAIRVO 2 during week 1, week 2, week 3 and week 4.
- iii. Average use per day on days of myAIRVO 2 use

Withdrawals and exclusions:

- i. Proportion of participants screened that were excluded
- ii. Reason for exclusion
- iii. Proportion of participants enrolled that were withdrawn
- iv. Reason for withdrawal

Participants requiring oxygen delivery via myAIRVO 2:

- i. Proportion of participants using domiciliary oxygen

Aspects of myAIRVO 2 use:

- i. Proportion of participants who reported having reduced myAIRVO 2 flow settings from the initial flow
- ii. Reduction in flow
- iii. Proportion of participants who reported having increased myAIRVO 2 flow settings from the initial flow
- iv. Increase in flow
- v. Proportion of participants who reported having reduced myAIRVO 2 temperature setting from the initial setting
- vi. NHF therapy Questionnaire results

Clinical outcomes

- i. Proportion of participants with at least one hospital readmission within 30 days of discharge
- ii. Reasons for hospital admissions (AECOPD, other respiratory cause or other cause)
- iii. In those that had at least one hospital readmission:
 - a. Number of readmissions
 - b. Time to first hospital readmission
 - c. Hospital readmission length
- iv. Proportion of participants with at least one ED visit within 30 days of discharge
- v. Reason for ED visits (AECOPD, other respiratory cause or other cause)
- vi. In those that had at least one ED visit:
- vii. Number of ED visits
- viii. Time to first ED visit
- ix. Proportion of participants with at least one GP visit within 30 days of discharge
- x. Reason for GP visits (AECOPD, other respiratory cause or other cause)
- xi. In those that had at least 1 GP visit within 30 days of discharge: number of GP visits
- xii. LACE Index for hospital admissions
- xiii. Lung function measurements (FEV₁, SVC_{in} and FVC) at day 1 and 31.

* An ED visit is counted if the patient went to ED for assessment and was not subsequently admitted to a hospital ward.

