9.10.3. Pre-discharge assessments and training

- a.** Participants will be approached at least one day prior to expected discharge to ensure familiarity with NHF therapy prior to discharge. Written informed consent will be obtained (see participant information sheets and consent forms).
- b.** Demographic data collection will include: Date of birth, gender, year of COPD diagnosis, presence of alpha antitrypsin deficiency, other respiratory conditions, current medications, pack year history (a pack year is defined as twenty cigarettes smoked every day for one year, for a calculator see <http://smokingpackyears.com/>), LACE index score and if domiciliary oxygen is prescribed. The Investigator will update the Medical History Log and Medication Log. The last recorded spirometric values in the participant's clinical records will also be documented.
- c.** Participant inclusion and exclusion criteria (Section 9.8) will be assessed, and ineligible patients excluded.
- d.** Participants will be allocated a myAIRVO 2 device and the device serial number will be recorded.
- e.** A training session on how to use myAIRVO 2 will be performed by the study investigator (Appendix 2). The participants' next of kin will be encouraged to be present at this session. Familiarization and acclimatization to the device and the therapy will also be conducted prior to leaving the hospital. Where possible any issues regarding the device or therapy will be addressed prior to discharge. The participant will also be given the myAIRVO 2 user manual and 'Quick guide sheet' to read prior to the home visit and a phone number to contact the investigator with any questions during business hours.
- f.** For participants on oxygen only: If possible, oxygen saturation testing on the participant's usual home oxygen flow will take place during the hospital admission. The participant will be placed on their home oxygen prescription while sitting at rest for at least 5 minutes. Should the participant's oxygen saturation levels on their prescribed oxygen be $<88\%$ or $\geq 95\%$ they will be withdrawn from the study and referred for review of their home oxygen prescription.

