9.10.4. Post-discharge methods

- a.** A home visit will be made by an investigator on the day of or day after discharge. The investigator will:
- i. Ensure the equipment is set up correctly and reinforce the previous training on myAIRVO 2. (Appendix 1).
 - ii. Check participants will have the myAIRVO 2 user manual and the 'Patient summary sheet' as an easy reference for device use.
 - iii. Perform lung function tests using a spirometer (Jaegar pneumotac spirometer with J-Lab software) according to ATS/ERS Taskforce standards.^{10 11} Participants will not be required to withhold bronchodilator medication prior to testing. The drug, dose and time of the last administration prior to spirometry will be recorded. This will inform COPD severity of participants and baseline lung function measurements.
- b.** Participants on domiciliary oxygen will have oxygen saturations recorded on simple nasal prongs according to their existing prescription. NHF therapy will then be initiated and oxygen will be titrated through myAIRVO 2 to determine the flow of oxygen delivery required to achieve the same oxygen saturation level (Section 9.10.04).

c. myAIRVO 2 devices will electronically record data on the date and time the device was used. Should participants change the flow of their myAIRVO 2 device (participants without domiciliary oxygen only) or alter the temperature, they will be asked to document this in their diary.

d. On the 3rd, 7th, 14th and 21st and 28th day post discharge the investigator will contact the participant by phone. Participants will be asked:

- i. If they are having any problems using myAIRVO 2.
- ii. If they have needed to return to the hospital, the reason and length of their hospital visit. These details will be checked against hospital records. In addition, they will be asked if they have needed to visit their GP or other allied health care practitioners and the reason. The Investigator will complete the CRF and the medical history log, concomitant medications log, medical contact log, adverse event/ serious adverse event forms as required.

e. On the 31st day post discharge an investigator will perform a home visit or the participant will visit the study investigator at their clinic office.

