- i. When the investigator contacts the participant on day 28th day post discharge they will confirm with the participant the home /office visit time on the 31st day post discharge and that their last period of myAIRVO 2 use is to commence on day 30 (the day before the home/office visit).
- ii. At the home/office visit the NHF therapy Questionnaire will be administered.
- iii. Participants will be asked whether they have had any hospital admissions and the length and cause for any admissions. These details will be checked against hospital inpatient records. In addition they will be asked if they have visited their GP or other allied health care practitioners. The Investigator will complete the CRF and the medical history log, concomitant medications log, medical contact log, adverse event/ serious adverse event forms as required.
- iv. Lung function will be performed using a spirometer (Jaegar pneumotac spirometer with J-Lab software) according to ATS/ERS Taskforce standards.^{10 11} Participants will not be required to withhold bronchodilator medication prior to testing. The drug, dose and time of the last administration prior to spirometry will be recorded. This will inform if lung function has improved during the study.
- v. The myAIRVO 2 device and associated equipment will be collected from the participant.

9.10.5. myAIRVO 2 domiciliary oxygen assessment and prescription

a. The participant will have their prescribed domiciliary oxygen flow rate recorded.

b. Oxygen saturation levels will be measured (Point A) by oximetry after at least 5 minutes at rest using standard nasal prongs with oxygen administered according to their prescription (Flow A). Should the participant's oxygen saturation levels be <88% or ≥95% they will be withdrawn from the study and referred for review of their home oxygen prescription.

c. NHF therapy will then be administered to the participant by myAIRVO 2 set at a flow rate of 25L/minute with supplemental oxygen delivered at Flow A for at least 5 minutes whilst the participant is at rest. Oxygen saturation levels will then be recorded.

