11. STATISTICAL CONSIDERATIONS

11.1. Description of the Statistical Design

As this is a feasibility study the primary outcome variable (9.4.1) will be expressed as the mean number of hours per day used, with standard deviation. The mean may be weighted for time in the study and allocated 95% confidence intervals for each by weighted regression.

Continuous outcomes 9.4.2-4, 9.4.11, 9.4.13, 9.4.18c, and 9.4.26 will also be expressed as mean, standard deviation. Means may be weighted for time in the study and allocated 95% confidence intervals for each by weighted regression.

For the mean number of hospital readmissions (9.4.18a), ED visits (9.4.21a) and GP visits (9.4.24) Poisson regression will be used.

Time to first hospital readmission (9.4.18b) and first ED visit (9.4.21b) will be analyzed by Kaplan-Meier survival estimates and CI for quantiles of survival, those who don't get admitted within the study time will be censored data.

Categorical outcomes 9.4.5-10, 9.4.12, 9.4.14, 9.4.16, 9.4.17, 9.4.19, 9.4.20, 9.4.22, 9.4.23 and 9.4.25 will be described by absolute numbers and proportions. Confidence intervals may be calculated for outcomes 9.4.5-10, 9.4.12, 9.4.14, 9.4.16, 9.4.19, and 9.4.22.

NHF questionnaire results (9.4.15) will likely be presented by mean, standard deviation and confidence interval, however if the data distribution is heavily skewed data may be presented as proportions.

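### Day 1 and day 31 spirometry set no interval from the last bronchodilator dose and 11.1 does not use the recorded dose times, so the question of improved lung function is open to timing differences (minor, secondary outcome)

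*Combined protocol and SAP*

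**What the plan says.** Section 9.4 lists as its last clinical outcome "Lung function measurements (FEV₁, SVC_{in} and FVC) at day 1 and 31". Counting the 9.4 list in order makes this item 9.4.26, the number used in 11.1.

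Section 9.10.4 describes the two tests, at a.iii (home visit on the day of discharge or the day after) and e.iv (day 31, at home or at the clinic office). Both carry the same rule, "Participants will not be required to withhold bronchodilator medication prior to testing", and the same record, "The drug, dose and time of the last administration prior to spirometry will be recorded". Neither sets a dose-to-test interval or a clock time, and neither ties the day 31 test to the conditions of the first.

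The stated purposes differ. For the first test: "This will inform COPD severity of participants and baseline lung function measurements". For day 31: "This will inform if lung function has improved during the study".

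The analysis in 11.1 is: "Continuous outcomes 9.4.2-4, 9.4.11, 9.4.13, 9.4.18c, and 9.4.26 will also be expressed as mean, standard deviation". The only refinement offered is optional: "Means may be weighted for time in the study and allocated 95% confidence intervals for each by weighted regression". The recorded drug, dose and time appear in no analysis, and neither 9.4 nor 11.1 defines a day 31 minus day 1 change. Section 9.2 has no control group, and 9.3 treats bias as not relevant to the study.

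**The concern.** Whether lung function improved is a within-person question. Under the present rule a participant may be tested soon after a dose at one visit and many hours after a dose at the other. The observed change then contains the true change plus the difference in bronchodilator effect at the two tests. There is no control arm in which a shared shift in timing would cancel.

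The two consequences need to be kept apart:

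- **Noise.** If timing varies haphazardly, individual changes become more variable but the mean change is not biased.
- **Bias.** If average timing, or the drug or dose, differs between visits, the mean change is shifted. This is plausible, because the first test comes straight after an exacerbation admission and at home, while day 31 may be at a clinic office. Nothing in the documents shows that it occurs.

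At stake is how one secondary outcome can be read. The information needed to examine the problem is already being collected, and the plan gives it no use.

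**Working it through.** **The plan's own figure.** Section 11.2 needs at least 80 patients and expects 20% drop-out: 80 / (1 - 0.20) = 100, which matches the stated 20 + 80. It does not depend on spirometry, so nothing below changes it. The documents give no SD, effect size or bronchodilator response for lung function.

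**Assumed inputs (none from the documents).**
- FEV1 bronchodilator response R: 0.10 to 0.20 L.
- SD of FEV1 change without timing differences, s: 0.15 to 0.25 L.
- Shares of participants tested within the effective window at day 1 and day 31: p1 and p31.
- n = 80, the minimum in 11.2.

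**Sampling error for comparison.** The 95% half-width is 1.99 × s / √80. For s = 0.15 it is 0.033 L; for s = 0.25 it is 0.056 L.

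**Noise, with random timing.** Take the effect as fully present or absent, independent between visits, with p1 = p31 = 0.5. The timing component of the change has SD = R × √(0.25 + 0.25), which is 0.071 L for R = 0.10 and 0.141 L for R = 0.20. Variances add, so the total SD is √(s² + component²):

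| R (L) | s (L) | total SD (L) | rise (L) |
|---|---|---|---|
| 0.10 | 0.15 | √(0.0225 + 0.005) = 0.166 | 0.016 |
| 0.10 | 0.25 | √(0.0625 + 0.005) = 0.260 | 0.010 |
| 0.20 | 0.15 | √(0.0225 + 0.020) = 0.206 | 0.056 |
| 0.20 | 0.25 | √(0.0625 + 0.020) = 0.287 | 0.037 |

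The SD rises by about 0.01-0.06 L. Full-or-none timing is close to a worst case. In a milder model the effect present at each test is uniform between 0 and B, with B = 0.05-0.20 L. The component is then √(2B²/12) = 0.020-0.082 L, and the half-width (using 1.96) moves only from 0.033-0.055 L to 0.033-0.058 L.

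**Bias, with systematic timing.** Bias in the mean change = R × (p31 - p1).
- p1 = p31 = 0.5: zero for any R.
- p1 = 0.7, p31 = 0.4: -0.03 to -0.06 L.
- p1 = 0.8, p31 = 0.4: -0.04 to -0.08 L.

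The size is proportional to the assumed gap between visits, and the sign reverses if more participants are within the window at day 31. A gap of 0.3-0.4 gives a bias of the same order as the half-width, in some combinations larger.

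**The case against.** Several points on the other side stand.

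- The no-withholding rule and the record of drug, dose and time are the same at both visits, so intervals can be reported or adjusted for without new data. Both tests also follow cited ATS/ERS standards, which are not available here. How far those address timing is unknown; the protocol's own wording leaves it open.
- No comparison is formally planned. Section 11.1 gives a mean and SD, and the question of improvement rests on one purpose sentence in 9.10.4e.iv. That sentence does state a purpose, and no analysis is defined to serve it.
- Even with perfect matching, recovery after the exacerbation in an uncontrolled study prevents reading the change as a device effect.
- Booking an appointment cannot set the time since an as-needed dose, so matching can be asked for only where feasible and against regularly scheduled medication.

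A reader might also infer more than the documents support:

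- **That the SD for the later randomised trial is compromised.** Section 7.2 says that trial is to be powered on readmission rates, and none of the five objectives in 8.2 names lung function.
- **That COPD severity is shifted towards worse disease.** A recent exacerbation may lower the first reading, but a recent dose would raise it. The net direction is unknown.
- **That severity should instead come from the clinical record.** Section 9.10.3b collects "The last recorded spirometric values in the" participant's records, but requires neither their date nor the bronchodilator state. They are not clearly better.

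**Conclusion.** The point holds as a minor improvement to a secondary outcome. The documents establish that no dose-to-test interval is set, that the visits are not matched, that the recorded dose information is unused, and that the stated question about improvement has no defined paired analysis.

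They do not establish that the mean change is biased. That requires average timing to differ between visits, which is assumed here. On the stated assumptions the cost is a rise of about 0.01-0.06 L in the SD of individual change under random timing. The bias is 0 to 0.08 L in absolute size under the assumed systematic shifts, against a half-width of about 0.03-0.06 L at n = 80. The stronger claim, that dose timing does hide or reverse a real change, would follow only from chosen inputs. Device hours per day and the target of 100 participants are unaffected.

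**What to change.** 1. **Section 9.10.4e.** The day 28 call already confirms the day 31 visit time. Add that, where feasible, the day 31 test is booked at a similar time of day to the day 1 test. It should also fall at a similar interval after the participant's regularly scheduled bronchodilator as recorded at day 1. State that no medication is withheld or changed for this.
2. **Section 11.1.** For 9.4.26, define the paired day 31 minus day 1 change in FEV1, SVCin and FVC. Report the dose-to-test interval at each visit. Add one sensitivity analysis of the change, either adjusted for the between-visit difference in interval or restricted to participants whose intervals were similar. Define similar in advance.
3. **Interpretation.** State that recovery after the exacerbation, with no control group, still prevents reading the change as an effect of the device.

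The cost is a few sentences, slightly less freedom in scheduling day 31, and fewer participants in a restricted analysis. No new test or data item is needed. Adjustment on recorded intervals removes the timing effect only in part; alignment at booking does more where it can be achieved.

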9.11. Withdrawal Criteria

Participants are able to stop the intervention at any time, without being withdrawn from subsequent portions of the study. Participants may withdraw from the entire study at any time without giving a reason. Participants may be withdrawn at the discretion of the Investigator for any reason that is believed may present a safety risk.

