11.6. Selection Criteria

For endpoint details see section 9.4. All participants who were screened to take part in the study will be included in the analysis of endpoint 2.b.i. All patients who were discharged with a myAIRVO 2 device to take home will be included in analysis of all other endpoints.

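### Day 31 spirometry is meant to show whether lung function improved, but section 11.1 plans only a mean and SD of the measurements, with no paired change and no valid interval for it

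*Combined protocol and SAP*

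**What the plan says.** Section 9.10.4 gives each spirometry session a purpose. Of the first, at the home visit around discharge, a.iii says: "This will inform COPD severity of participants and baseline lung function measurements". Of the second, on day 31, e.iv says: "This will inform if lung function has improved during the study". Read together, these describe a before-and-after comparison.

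The endpoint in section 9.4 (Clinical outcomes, xiii) is narrower: FEV1, inspiratory SVC and FVC, ending "FVC) at day 1 and 31". It names levels at two visits, not a change.

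Section 11.1 covers it in one line: "Continuous outcomes 9.4.2-4, 9.4.11, 9.4.13, 9.4.18c, and 9.4.26 will also be expressed as mean, standard deviation". It then adds: "Means may be weighted for time in the study and allocated 95% confidence intervals for each by weighted regression". Both the weighting and the intervals are optional, and the intervals are for means.

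On who is analysed, section 11.6 says: "All patients who were discharged with a myAIRVO 2 device to take home will be included in analysis of all other endpoints". Section 9.11 allows loss before day 31 ("Participants may withdraw from the entire study at any time without giving a reason") but also allows people to stop the device and stay in follow-up ("Participants are able to stop the intervention at any time, without being withdrawn from subsequent portions of the study"). Section 12.2 expects some deaths and some deterioration.

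No section names a change score, a paired or repeated-measures analysis, or a rule for participants with only one of the two tests.

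**The concern.** Whether lung function improved is a question about change within people. A mean and SD at each visit describe two cross-sections. They omit the correlation between a person's two values, which determines how precisely the mean change is known. A reader of the planned tables could subtract one mean from the other, but could put an interval around the result only by treating the visits as independent groups.

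The second problem is who contributes. If the day 1 mean uses everyone tested and the day 31 mean only those who remain, the difference mixes change with selection.

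The study is meant to inform a later randomised trial, and section 11.2 wants it to be informative about suitable outcome measures. The SD of change is what one would need to judge spirometry for that role, and separate visit summaries do not supply it. The documents do not say that lung function will be an outcome of that trial, so this is a missed opportunity rather than a failed objective.

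**Working it through.** **1. Is 9.4.26 lung function?** The list in 9.4 is not numbered through, so count it in order: primary outcome 1; other use variables 2-4; withdrawals and exclusions 5-8; oxygen 9; aspects of use 10-15; clinical outcomes from 16. Items vii and viii are the two sub-items of the ED entry (21a and 21b in 11.1), so xiii is item 26. The count agrees with 11.1, which calls 9.4.15 the questionnaire and 9.4.24 GP visits.

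**2. Reproduce the plan's own figure.** Section 11.2 needs at least 80 patients and allows 20% drop-out: 80 / (1 - 0.20) = 100, matching 20 + 80. No SD, correlation or target precision for lung function is given, so what follows is in units of the SD at one visit, assumed equal at both.

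**3. Interval from separate means**, treated as independent, with 100 people on day 1 and 80 on day 31:

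half-width = t(0.975, 178) x sqrt(1/100 + 1/80) = 0.296 SD.

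With 80 at both visits it is t(0.975, 158) x sqrt(2/80) = 0.312 SD.

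**4. Interval from paired change** in 80 people with both tests, where r is the assumed within-person correlation:

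half-width = t(0.975, 79) x sqrt(2(1 - r)/80).

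| r (assumed) | paired half-width (SD) | 0.296 / paired |
|---|---|---|
| 0.5 | 0.223 | 1.3 |
| 0.8 | 0.141 | 2.1 |
| 0.9 | 0.100 | 3.0 |
| 0.95 | 0.070 | 4.2 |

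The same visit means and SDs are compatible with every row, so the planned output cannot tell a reader which applies.

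**5. Does the optional weighting help?** No. Weighting by time in the study changes how much each person counts towards a mean. It does not link a person's two tests.

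**6. Different people at the two visits.** Let a fraction f of those tested on day 1 lack a day 31 test, and let g be the day 1 gap between completers and those lost. With no true change in anyone and no weighting:

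shift = completer mean - [(1 - f) x completer mean + f x (completer mean - g)] = f x g.

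With f = 0.20 and an assumed g of 0.5 SD, the shift is 0.20 x 0.5 = 0.10 SD. With f = 0.10 it is 0.05 SD. If g = 0 it is zero. The 20% is an upper case: it is total drop-out, some withdrawals precede the first test, and people who stop the device may still attend on day 31. The documents give no value for g, so this shows the mechanism and is not an estimate.

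**The case against.** The strongest reply is that endpoint and analysis agree. Section 9.4 defines measurements at two days and 11.1 summarises measurements. Improvement appears only in a sentence describing a visit procedure, and spirometry is not named in the five objectives of section 8.2. This stands. It limits the weight of the point, but the protocol still states a use for the day 31 test that its planned summaries do not serve.

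A reader might infer that the plan yields no estimate of change at all. That goes too far. The two means can be subtracted, and if the same people are tested at both visits the result equals the mean paired change. What is missing is a valid interval and a rule on having both tests.

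A reader might also infer that the question cannot be answered. That is not supported either. Both tests are collected per participant, the study team will hold the pairs, and section 11.5 allows departures from the plan if they are described and justified. The gap is in the written analysis, not the data.

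Finally, the plan prescribes no independent-groups interval, so the ratios do not measure an error in a planned analysis. This is also correct. They show only what a reader limited to the planned summaries could construct.

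**Conclusion.** The point holds as a minor one. The protocol says day 31 spirometry will inform whether lung function improved, and 11.1 provides a crude difference of means at best, with no valid interval and no assurance that the two means come from the same people.

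The illustrated loss of precision is a factor of about 1.3 to 4.2. It rests on assumed correlations of 0.5 to 0.95, equal SDs at the two visits, and 100 people tested on day 1 falling to 80 on day 31. The possible selection shift has no size that the documents can fix, and it may be zero.

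The endpoint is secondary, in an uncontrolled feasibility study without pass/fail criteria (sections 9.2 and 11.3). Nothing here touches the primary outcome or the sample size. Nor would a paired interval make the change a device effect: participants are recovering from an exacerbation and there is no comparison group.

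**What to change.** In section 11.1, add for item 9.4.26:

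- the within-participant change, day 31 minus day 1, for FEV1, inspiratory SVC and FVC in participants with both tests, with mean, SD and 95% confidence interval;
- the number tested at each visit and the number of pairs;
- a table of day 1 values for those with and without a day 31 test.

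State alongside that the result applies to completers and is an uncontrolled change during recovery, so it is descriptive and not evidence of a device effect. The visit means and SDs already planned can stay.

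The cost is one or two sentences in 11.1 and one paired summary per spirometry measure. No new data are needed. The drawback is the restriction to completers, which the day 1 table makes visible but does not remove.
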